#### 10.4. Protocol Deviations Excluding Patients from the PPS

PDID	Description of Protocol Deviation
1.05, 1.06, 1.08	Inclusion Criteria 4, 5, and 7 not met but subject randomized
2.11	Exclusion Criteria 10 met but subject randomized
3.02	Baseline visit not performed
3.16	Screening visit was not performed
5.14	WOMAC patient assessment was not administered at Week 24 Primary Endpoint Analysis
8.04	Rescue medication administered during a protocol-prohibited period prior to scheduled visit during treatment period
8.05	Use of opioid medications anytime during treatment period
8.06	Use of non-protocol specified NSAIDs any time during the treatment
F.02	Confirmed treatment unblinding (in error)

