### 2.2. Sample Size and Power Considerations

Assuming a 2-sided alpha level of 0.05 and a 20% dropout rate up to week 24, an enrollment of 600 patients in the fasinumab 1 mg Q4W group and 300 patients in the placebo group will provide at least 99% power to detect an effect size of 0.46 in the WOMAC pain and physical function subscale scores (i.e., absolute treatment difference of 1.1 between fasinumab and placebo with a SD of 2.4). The assumed treatment difference and standard deviation (SD) are based on results from study R475-PN-1227. The sample size will provide 99% power to detect

an effect size of 0.36 in PGA (i.e., absolute treatment difference of 0.4 with a SD of 1.1, R475-PN-1227).

Assuming a 2-sided alpha level 0.05 and a 20% dropout rate up to week 24, an enrollment of 600 patients in the fasinumab 1 mg Q4W group and the pooled NSAIDs group will provide approximately 92% power to detect an effect size of 0.22 in the WOMAC pain subscale (i.e., absolute treatment difference of 0.51 with a SD of 2.3, [Schnitzer 2015]). The sample size will provide 95% power to detect an effect size of 0.24 in WOMAC physical function subscale (i.e., absolute treatment difference of 0.50 with a SD of 2.1, [Schnitzer 2015]), and 79% power to detect an effect size of 0.18 in PGA (i.e., absolute treatment difference of 0.18 with a SD of 1.0 [Ekman 2014]).

The sample size has been revised from 2700 patients in the previous amendments to approximately 1620 patients in amendment 4 due to the discontinuation of fasinumab 3 mg Q4W and 6 mg Q8W dose regimens. There will be approximately 600 patients randomized to the fasinumab 1 mg SC Q4W group, 300 patients randomized to the each of the NSAID groups, and 300 patients randomized to the placebo group (a total of 1500 patients). In addition, approximately 60 patients each were enrolled in the fasinumab 3 mg SC Q4W and 6 mg SC Q8W groups under earlier versions of the protocol before dosing was discontinued in these treatment groups.

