#### 3.4. The Safety Analysis Set (SAF)

The safety analysis set (SAF) includes all randomized patients from the FAS who received any study drug; it is based on the treatment received (as treated). Treatment compliance/administration and all clinical safety variables will be analyzed using the SAF including patients randomized to fasinumab 1 mg Q4W, NSAIDs, and placebo.

Determination of 'as-treated' will be performed in the following stepwise manner:

- If a patient receives at least one dose of fasinumab, 'as treated' implies the patients data will be analyzed under the fasinumab arm.
- If a patient receives no doses of fasinumab and was ever dispensed NSAIDs, 'as treated' implies the patients' data will be analyzed under the NSAID arm.
- If a patient receives no doses of either fasinumab or NSAID, the patients data will be analyzed under the placebo arm.

Safety data from patients randomized to fasinumab 3 mg Q4W or 6 mg Q8W will not be included in the main safety analysis summaries, but will be summarized in separate tables.

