### Per Protocol Set Analysis

Sensitivity analyses based on the PPS will be performed using the same approach as specified for the primary analysis in the beginning of this section. Values of the stratifying variables utilized for analysis on the PPS will be those captured in the EDC system.

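### The per-protocol set drops a patient for one acetaminophen dose before any treatment visit but has no exclusion for wrong study drug or substantial missed dosing

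*SAP*

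**What the plan says.** SAP 3.3 builds the PPS from full analysis set (FAS) patients who finish the 24-week treatment period and have none of the deviations in SAP 10.4. Its use is confined to sensitivity analysis. SAP 1.2.4 explains that the list was narrowed from major deviations to relevant ones.

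Item 8.04 on that list is "Rescue medication administered during a protocol-prohibited period prior to scheduled visit during treatment period". It has no minimum count, no dose threshold and no named visit. By contrast, item 5.14 is tied to the endpoint visit: "WOMAC patient assessment was not administered at Week 24 Primary Endpoint Analysis". The other items cover selected eligibility failures, missing screening or baseline visits, opioid use (8.05), non-protocol NSAID use (8.06) and unblinding in error (F.02). None concerns the study drug actually received or the amount taken.

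Protocol 7.2 sets the prohibited period at 24 hours before each scheduled visit in the treatment period, and gives protection of the efficacy measurements as the reason. It also allows acetaminophen for headache or fever.

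On the analysis, SAP 5.7.1 states: "Sensitivity analyses based on the PPS will be performed using the same approach as specified for the primary analysis". That approach is multiple imputation followed by an MMRM with treatment-by-visit terms and an unstructured covariance. The primary estimand in the same section disregards rescue use.

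**The concern.** The endpoint is Week 24. Every PPS patient has completed treatment and, through item 5.14, has a Week 24 WOMAC. With treatment-by-visit means and an unstructured covariance, the Week 24 contrast then rests essentially on Week 24 scores. A dose taken before an earlier visit does not affect the score being compared, yet it removes the patient.

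Rescue use also follows pain. SAP 4.5.3 compares it between arms as an exploratory efficacy outcome. Excluding on it conditions on a post-randomization variable that treatment may change, so the exclusions can be related to outcome and can differ by arm.

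In the other direction, a patient given the wrong kit, or one who missed several injections but finished 24 weeks, meets no exclusion. The PPS is drawn from the FAS, which is grouped as randomized, and SAP 3.3 does not regroup it by drug received, so such a patient counts under the randomized arm.

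What is at stake is how the check can be read. Agreement or disagreement between PPS and FAS could reflect who was removed for rescue use rather than what happens in patients who received their assigned treatment.

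**Working it through.** **1. Are the omitted events foreseen?** Yes, in four places.
- Drug other than assigned: SAP 3.4 has as-treated rules, beginning "If a patient receives at least one dose of fasinumab", and Protocol 10.4.1 plans a listing of patients not treated as randomized.
- Skipped injections: under Protocol 7.1 a subcutaneous dose outside its window is not given and the patient continues.
- Withheld injections: under Protocol 7.3.2.2 subcutaneous drug is held during adjudication or specialist review, while oral drug may continue.
- Low intake: SAP 5.6.1 defines compliance for injections and capsules, but only for descriptive summary on the safety set.

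**2. The plan's own power figures.** SAP 2.2 is the source: "Assuming a 2-sided alpha level of 0.05 and a 20% dropout rate up to week 24", with "600 patients in the fasinumab 1 mg Q4W group and 300 patients in the placebo group". After 20% dropout this is 600 × 0.8 = 480 and 300 × 0.8 = 240. Power = Φ(Δ/SE − 1.96), with SE = SD × √(1/n₁ + 1/n₂).
- WOMAC against placebo, "absolute treatment difference of 1.1 between fasinumab and placebo with a SD of 2.4": SE = 2.4 × √(1/480 + 1/240) = 0.190, power 99.99% (stated: at least 99%).
- WOMAC pain against pooled NSAIDs, "absolute treatment difference of 0.51 with a SD of 2.3": SE = 2.3 × √(2/480) = 0.148, power 93.0% (stated: about 92%).
- The other three reproduce as well: 99.6% (99%), 95.8% (95%) and 79.6% (79%).

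The documents give no PPS size or PPS power to compare with.

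**3. Loss from 8.04 alone.** There are six post-baseline clinic visits: Weeks 4, 8, 12, 16, 20 and 24. The Week 2 phone contact is left out; counting it would raise the loss. Let p be the chance of rescue use in the 24 hours before a given visit. It is not in the documents and is assumed here to lie between 1% and 20%, equal in the arms and independent across visits. Share kept = (1 − p)⁶; share kept if 8.04 applied to Week 24 only = 1 − p; SE factor = 1/√(share kept). The start is 480 fasinumab and 240 placebo completers.

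| p | Kept | Removed | Fasinumab / placebo | SE factor | Kept, Week 24 only |
|---|---|---|---|---|---|
| 1% | 94.1% | 5.9% | 452 / 226 | 1.03 | 99% |
| 2% | 88.6% | 11.4% | 425 / 213 | 1.06 | 98% |
| 5% | 73.5% | 26.5% | 353 / 176 | 1.17 | 95% |
| 10% | 53.1% | 46.9% | 255 / 128 | 1.37 | 90% |
| 20% | 26.2% | 73.8% | 126 / 63 | 1.95 | 80% |

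Clustering within patients lowers the loss. Under a beta-binomial model with an assumed intraclass correlation of 0.2 or 0.4, the share removed is 18.4% or 13.5% at p = 5%, and 33.9% or 25.6% at p = 10%.

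Power for a difference of 1.1 against placebo stays at 99.9% (p = 5%), 98.8% (10%) and 84% (20%). For 0.51 against pooled NSAIDs, if that contrast is run in the PPS at all, it falls from 93% to 84%, 71% and 42%.

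**4. Arms that differ.** If p were 10% on placebo and 5% on fasinumab, 0.90⁶ = 53% of placebo and 0.95⁶ = 74% of fasinumab completers would remain. The removals would be 47% against 26%.

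**5. Direction.** In an illustrative simulation (true difference 1.1, SD 2.4), the per-visit chance of rescue rose with the Week 24 score on the logistic scale, and p was set at the placebo mean. With a slope of 0.5 per SD the PPS difference was 1.07 (p = 2%), 1.03 (5%), 0.98 (10%) and 0.92 (20%). With a slope of 1.0 at p = 10% it was 0.82. Runs with zero slope gave 1.095 to 1.115, which shows the simulation noise. In these scenarios the shift is toward zero.

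**The case against.** **The 24-hour rule has a purpose.** It protects efficacy scores, and the primary approach also presents estimates at earlier visits, where rescue could matter. This stands: a rescue exclusion is not arbitrary. It justifies excluding the affected score, but not discarding an unaffected Week 24 score.

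**Gross non-compliance is handled elsewhere.** Protocol 7.3.2.1 stops study drug for continued non-compliance after counselling, and capsules are counted at each treatment clinic visit. A patient taking no capsules should therefore often be found, discontinued and so fall outside the PPS. This stands in part. It depends on site action, and it does not cover wrong-kit errors or injections skipped or withheld under the protocol's own rules.

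**Any per-protocol set conditions on post-randomization events.** The completion requirement does so too, and the plan uses the PPS for sensitivity only. This stands, and it limits the weight of the point.

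Three stronger readings are tempting, and the documents do not support them.
- A reader might infer that the PPS does not test adherence. It does in part: it requires 24 weeks of treatment and excludes opioid and non-protocol NSAID use.
- A reader might infer that NSAID-arm patients who skip capsules dilute the NSAID contrast. The tested contrast is fasinumab against pooled NSAIDs, with fasinumab assumed better by 0.51, so NSAID non-takers would tend to widen it. SAP 10.1 also assigns the PPS only to the co-primary endpoints, while SAP 3.3 mentions selected secondary endpoints without naming them.
- A reader might infer a large, known loss. The rescue rate is assumed throughout.

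**Conclusion.** The point holds in a limited form. On its wording, item 8.04 removes a patient for one acetaminophen dose before any treatment-period visit, and no item covers drug other than assigned or substantial missed dosing. Following the list would drop patients with a sound Week 24 score and could keep patients who did not receive their assigned treatment.

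The size is not established. Under independence across six visits the loss runs from about 6% (1% per visit) through 26% (5%) to 47% (10%), and clustering reduces it. The difference between arms and the shift toward zero are illustrations that rest on assumed rates and slopes.

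The effect is confined to the PPS sensitivity analysis. The FAS primary analysis, the treatment-policy and tipping-point analyses and the control of type I error are untouched, so nothing here weakens the main conclusion. Severity is minor; the change is a cheap improvement.

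**What to change.** Amend SAP 10.4 before unblinding:
- Limit 8.04 to the Week 24 visit, as 5.14 is. Alternatively, keep the patient and set only the affected visit's score to missing; in that case, state how a Week 24 score set to missing relates to 5.14.
- Add an exclusion for study drug received other than as randomized.
- Add a minimum-exposure item based on the injection and capsule compliance measures in SAP 5.6.1, with a threshold chosen by the sponsor and fixed in advance. The documents offer no basis for a particular value.

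The cost is a few lines. The diary, dispensing and injection data are already collected, and SAP 1 allows revision on blinded review before lock. There are two downsides. Under the first option, some retained patients will have early-visit scores affected by rescue. Exclusion for rescue just before Week 24 also remains related to outcome: limiting 8.04 cuts the number removed without ending that dependence. Reporting the number excluded under each item, by arm, would let readers judge it.

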### 10.5. OMERACT – OARSI RESPONDER CRITERIA

Note that the criteria in the diagram above are based on standardized scores between 0 and 100. For this study, WOMAC pain and physical function score are between 0 and 10, so the absolute change required for response is the required change in the diagram above divided by 10; PGA is 1, 2, 3, 4 or 5, so the absolute change required for response is at least 1 point.

Signature Page for VV-RIM-00105092 v1.0

ESig Approval	[Redacted] 000
---------------	----------------

ESig Approval	[Redacted] 000
---------------	----------------

ESig Approval	[Redacted] 20 21:23:06 GMT+0000
---------------	---------------------------------

ESig Approval	[Redacted] 000
---------------	----------------

ESig Approval	[Redacted] -2020 11:18:46 GMT+0000
---------------	------------------------------------

ESig Approval	[Redacted] -2020 12:11:47 GMT+0000
---------------	------------------------------------

Signature Page for VV-RIM-00105092 v1.0 Approved
